Preliminary Data. The pilot data to justify the current trial was a dose-response study that randomized 39 subjects with stage I-III colon cancer to 150 min/wk or 300 min/wk of aerobic exercise or a usual-care control group for 24 weeks.⁴⁸ We identified an interaction between cancer stage (a randomization stratification factor in the pilot study) and randomized group for changes in high-sensitivity [hs]-CRP ($P_{\text{interaction}}=0.051$) and IL-6 ($P_{\text{interaction}}=0.002$). Compared to baseline, 150 min/wk exercise reduced hs-CRP ($-0.79\pm 0.38 \text{ mg/L}$; $P=0.038$) and IL-6 ($-0.57\pm 0.29 \text{ pg/mL}$; $P=0.047$) in subjects with stage III but not in subjects with stage I/II disease. Compared to baseline, 300 min/wk of aerobic exercise did not reduce hs-CRP or IL-6. Additional analyses demonstrated that compared to baseline, 150 min/wk of aerobic exercise reduced fasting plasma insulin ($-28.0\pm 8.4 \text{ pmol/L}$; $P=0.001$) and glucose ($-0.39\pm 0.1 \text{ mmol/L}$; $P=0.011$),⁴⁹ and CTCs ($-1.3\pm 0.3 \text{ cells/mL}$; $P<0.001$).⁵⁰ However, due to the multiple randomized groups of this pilot trial, the sample size within each group was small ($n=12-14$), making between-group comparisons statistically underpowered. The results obtained from this pilot study inform the primary and secondary aims for the proposed trial, as detailed below.

Experimental Design & Methods

A. Number of Subjects

Accrual is 60 subjects (see power and sample size section below), recruited over 24 months, with a monthly accrual goal of approximately 2–3 subjects per month. In our prior trial, we successfully accrued 5.5 subjects per month.¹ Using estimates from our prior trial, we predict we will need to screen approximately 160 potential subjects to successfully randomize 60. We aim to recruit an equal ratio of males and females and ≥25% non-white minority subjects.

B. Inclusion and Exclusion Criteria

Many oncology clinical trials do not reach their minimum projected accrual goal.⁵¹ To ensure trial completion, we implement prospectively specified stepped inclusion and exclusion criteria that enable the efficient recruitment of the most homogeneous study population that is feasible within the allowable time horizon without compromising subject safety or scientific validity.

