We will begin with three months of strict eligibility criteria (Phase 1). At the end of three months, if six subjects are not accrued, eligibility criteria will be expanded for another three-month period (Phase 2). If, at the end of six months, we have still not accrued an average of two subjects per month, we will further expand eligibility criteria (Phase 3). We successfully implemented these prospectively specified stepped inclusion and exclusion criteria in the pilot study.⁴⁸

Phase 1 (most strict) inclusion criteria:

- 1.1 Age ≥18 years
- 1.2 Histologically-confirmed stage III colorectal cancer
 - a. Self-report during screening is acceptable if confirmed with pathology report, state tumor registry file, or physician documentation prior to randomization
- 1.3 Completed surgical resection within 1–24 months or completed chemotherapy (if applicable) within 1-24 months
- 1.4 Provide written approval by a physician or other qualified healthcare provider
- 1.5 No planned major surgery during the study period (including colostomy reversal; however, chemotherapy infusion port removal is permitted)
- 1.6 Readiness to exercise [as determined by a modified version of the Physical Activity Readiness Questionnaire (PAR-Q)]
 - a. If there are any indications that home-based exercise would be unsafe based on the PAR-Q, the patient will not be enrolled until approval from the patient's provider (e.g., oncologist, cardiologist) confirms that it is safe to exercise
- 1.7 Allow the collection and storage of specimens and data for future use
- 1.8 Willing to be randomized

Phase 2 (less restrictive) inclusion criteria will expand:

- 2.1 Histologically-confirmed stage to include stage I, II, or III colorectal cancer

- a. Self-report during screening is acceptable if confirmed with tumor registry, pathology report, or physician documentation prior to randomization
- 2.2 Time since completing surgical resection to 1–36 months or time since completing chemotherapy (if applicable) to 1-36 months

Phase 3 (least restrictive) inclusion criteria will expand:

- 3.1 Time since completing surgical resection \geq 1 month or time since completing chemotherapy (if applicable) \geq 1 month
- 3.2 Histologically confirmed stage I, II, or III colorectal cancer \geq 1 month since completing surgical resection or \geq 1 month since completing chemotherapy and/or radiotherapy

Exclusion criteria for all three accrual phases of recruitment include:

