Body Composition. Body mass, height, weight, waist, and hip circumferences will be assessed using a digital scale, scale-mounted stadiometer, and Gulick tape measure, respectively. DXA (Hologic) will be used to quantify changes in bone mineral density and body composition.

Accelerometry. Participants will be asked to wear an Actigraph GT3X+ triaxial accelerometer for one week before and after the study to objectively assess activity levels.

Clinical Characteristics. Clinical characteristics, including tumor pathology, surgical history, and chemotherapy treatment plan, will be obtained from the clinical and cancer registry data files prior to randomization.

Patient Outcomes. Participants will complete questionnaires relating to demographics, alcohol and smoking habits, current medicine, and supplement usage. Participants will complete a patient-reported version of the Common Terminology Criteria for Adverse Events.

Data and Specimen Banking

The participant will be asked to allow blood specimens and data to be stored and used for research at a later time. Participants who refuse to have this information kept for future research will be excluded from the study. The specimens and data will be stored indefinitely. Future research may take place at Pennington Biomedical and may involve Pennington Biomedical researchers in this study. The future research may not take place at Pennington Biomedical Research Center and may not be reviewed by Pennington Biomedical Research Center's Institutional Review Board.

For privacy and confidentiality, all specimens and scans will be labeled with a unique series of letters and numbers. Pennington Biomedical will store the information with this unique identifier. The research done with data from these specimens and scans may help to develop new products in the future or may be used to establish a diagnostic test that could be patented or licensed. The participant will not receive any financial compensation for any patents, inventions, or licenses developed from this research.

The de-identified data will be stored indefinitely on the network shares at PBRC. Hard copy records for each subject will be kept in the participant's chart located in the Medical Records Department. These data will be used in publications but not shared outside of the PI's.

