Long-term storage of specimens will be at -80° C. The samples will be stored in a designated freezer housed at Pennington Biomedical Research Center. The Principal Investigator, unless otherwise noted, will be the person who has access to the samples. Each sample will be labeled with the subject's ID and date.

Power analysis

After completion of baseline measurements, participants will be stratified by sex (male vs female) and then randomized in a 1:1 ratio to either the exercise or control group using a computer-generated algorithm. The co-primary outcomes for this study are hs-CRP and IL-6. For the CRP outcome, assuming a baseline concentration of 1.87 mg/L with a standard deviation of 1.32 mg/L, correlation of 0.8 between time points, a reduction of -0.71 mg/L in the exercise group over 12 weeks, and a type-I error rate of 5%, 46 participants total will provide 80% statistical power to detect between-group differences. For the IL-6 outcome, assuming a baseline concentration of 1.7 pg/mL with a standard deviation of 0.7 pg/mL, a correlation of 0.58 between time points, a reduction of -0.57 pg/mL in the exercise group over 12 weeks, and a type-I error rate of 5%, 48 participants will provide 80% statistical power to detect between-group differences. sTNF- α R2 is a secondary inflammatory measure. In the pilot study, we observed a 3% dropout rate (defined as participants not providing endpoint data), an 8% crossover rate (defined as control group participants who disclose initiating a structured, progressive exercise program during the trial), and 8% recurrence rate (defined as the clinical discovery of locoregional or distant metastatic disease).⁷⁰ We will inflate these estimates to accommodate a higher-than-anticipated dropout, experience a recurrence, and/or crossover. Enrolling 60 study participants provides a robust estimate of the largest necessary sample size needed for this trial. This sample size provides adequate statistical power to detect moderate between-group effect size differences (e.g., Cohen's d of ≥ 0.3) for measures of insulin resistance (Aim 2) and CTCs (Aim 3).

Statistical Analysis

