The primary hypothesis in this trial is that exercise will significantly lower plasma inflammation concentrations over 12 weeks compared to control. All inferential analyses will be conducted on an intention-to-treat basis. Plasma inflammatory concentrations will be log-transformed in the inferential analysis to improve normality. Changes in outcomes will be evaluated from baseline to follow-up in the two groups using a repeated-measures mixed-effects regression model that accounts for the correlation between repeated measures and is robust to missing data. The baseline value of the dependent variable and sex (randomization stratification factor) will be included as a covariate in the regression models.⁵⁵ Group-by-time interaction terms will be included as fixed effects in the regression model. Model fit will be assessed using standard methods. A closed testing procedure for the two study outcomes (hs-CRP and IL-6) will be used, which is hierarchically ordered to test CRP and then IL-6 to maintain the overall experiment-wise error rate at 5%.⁵⁶ Other inflammatory outcomes and measures of insulin resistance (Aim 2) and CTCs (Aim 3) will be analyzed using the same statistical techniques and reported at the nominal type I error rate of 5%.

Data and Specimen Management

Study participants will be assigned unique subject identification (ID) numbers. Study subject ID numbers will be used on all data collection instruments, including questionnaires, data collection forms, biological specimen tubes, and computer records. A master list linking the participants' names and ID numbers will be kept in a password-protected computer file with access restricted to the PI and co-PIs. Biological samples that are moved off-site for analysis will not contain any personally identifiable information and will be labeled with only the unique subject ID numbers. Staff at these sites will not have access to the master list at any time.

Data collection forms will be kept under lock and key or password-protected if computerized and under the control of the PI, co-PIs, and medical investigator. Only personnel assigned to the research study by the PI will have access to the data. Hard-copy data records will be stored for a minimum of three years after study completion.

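### Cancer stage, which modified the exercise effect in the pilot, is in neither the randomization strata nor the primary model; adding it as a covariate is a small, nearly free gain

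*Combined protocol and SAP*

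**What the plan says.** Preliminary Data reports, for changes in hs-CRP (P=0.051) and IL-6 (P=0.002), an "interaction between cancer stage (a randomization stratification factor in the pilot study) and randomized group". Reductions at 150 min/wk were seen "in subjects with stage III but not in subjects with stage I/II disease".

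Phase 1 eligibility is stage III only. If six participants are not accrued in three months, Phase 2 widens the criterion: "Histologically-confirmed stage to include stage I, II, or III colorectal cancer". Phase 3 keeps stages I-III, and the Objectives describe a stage I-III population of 60.

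Stage is known in time to be used. Eligibility requires it to be confirmed before randomization, and Clinical Characteristics says that tumor pathology "will be obtained from the clinical and cancer registry data files prior to randomization".

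Under Power analysis, "participants will be stratified by sex (male vs female) and then randomized in a 1:1 ratio". Under Statistical Analysis, "The baseline value of the dependent variable and sex (randomization stratification factor) will be included as a covariate in the regression models". Stage appears in neither place, and no stage-by-group or stage subgroup analysis is specified. The documents give no reason for dropping stage and cite no evidence that sex predicts response.

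**The concern.** The sponsor's own pilot singles out stage as a possible modifier of the exercise effect on both co-primary outcomes, and the staged eligibility rules suggest that this signal was taken seriously. With about 30 per arm and mixed stages, the exercise arm can by chance hold more or fewer of the patients expected to respond, and the estimate then moves with that share. Part of this variation could be removed with a variable already collected. Without a prespecified role for stage, any later look at it would be post hoc, although the question was foreseeable from the pilot.

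**Working it through.** **Inputs from the documents.** N = 60, 1:1. hs-CRP: SD 1.32 mg/L, r = 0.8, effect -0.71. IL-6: SD 0.7 pg/mL, r = 0.58, effect -0.57 (the same figure as the pilot stage III change). Type I error 5%, power 80%.

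**Assumptions, because the documents give no figure.** Stage III share 50% (range 30-70%), no effect in stage I/II, raw scale, two-sided test.

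**1. The plan's sample sizes.** n per arm = 2(1.96+0.84)²·SD²/Δ².
- hs-CRP: change-score SD = 1.32·√(2(1-0.8)) = 0.835. This gives 22 per arm (44 in total) by the normal formula and 46 by the t-test (power 80.5%). The stated 46 reproduces.
- IL-6: the stated 48 reproduces with the raw SD of 0.7, since 2·7.849·0.49/0.3249 = 23.7, so 24 per arm. Using r = 0.58 gives 40-42 on change scores. Neither calculation refers to stage.

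**2. Chance imbalance, 30 per arm, no stage stratification.**

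| Stage III in the sample | Gap ≥10 points | Gap ≥20 points |
|---|---|---|
| Each patient stage III with probability 0.5 (total varies) | 52% | 16% |
| Exactly 30 of 60 (total fixed) | 44% | 20% |
| Exactly 18 or 42 of 60 (30% or 70%) | 40% | 16% |

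The first two rows differ mainly because an even fixed total rules out a gap of exactly three patients. With 30 of 60, the standard deviation of the gap is 13 points.

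**3. What a gap does to the IL-6 estimate.** The average effect at 50% stage III is 0.5·(-0.57) = -0.285. At a fixed total, a 10-point between-arm gap puts the exercise arm 5 points from its expected share.
- 10-point gap: 0.05·0.57 = 0.0285 pg/mL, which is 10% of 0.285 and 0.0285/0.157 = 0.18 standard errors.
- 20-point gap: 0.10·0.57 = 0.057 pg/mL, which is 20% of 0.285.
- Typical shift (one SD): 0.065·0.57 = 0.037 pg/mL. Its share of the variance is (0.037/0.157)², about 5-6%, and the ordinary standard error already reflects it.

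**4. Precision gained by adjusting.** Simulation of a baseline-adjusted IL-6 model, residual SD = 0.7·√(1-0.58²) = 0.570, 60 patients, 50% stage III:

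| Model | Mean reported SE | Actual spread of estimates |
|---|---|---|
| Baseline only | 0.157 | 0.157 |
| + stage | 0.154 | 0.155 |
| + stage and centred group-by-stage term | 0.149 | 0.155 |

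The stage covariate gains about 1-2%. Power goes from about 42% to 44% at 50% stage III, and from 71% to 73% at 70%. The reported 0.149 for the centred term is right only for the average effect at exactly the sampled stage mix. Over repeated samples the spread stays at 0.155.

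**5. If stage is also prognostic.** Omitting a covariate that explains a share R² of the residual variance inflates the SE by 1/√(1-R²): 1.0%, 2.6% and 5.4% for R² of 2%, 5% and 10%. hs-CRP power at 60, 90.9% without stage, would become 91.4%, 92.2% and 93.5%. The documents give no value of R².

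**The case against.** The strongest reply is that nothing here is an error. Randomization keeps the test valid, the model includes its own stratification factor, and the choice of factors at N = 60 is a design judgement. The baseline value, which is in the model, supplies most of the available precision. The pilot evidence is thin: 39 patients in three arms of 12-14, an hs-CRP interaction at P=0.051, and within-group changes in a study the protocol itself calls underpowered for between-group comparison. It shows possible effect modification, not that stage is prognostic. If accrual had stayed in Phase 1, no imbalance could arise. All of this stands. It limits the size of the point but does not remove it, because the Objectives expect stages I-III and the covariate costs almost nothing.

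Four stronger readings are tempting but not supported:
- **That imbalance biases the result or makes it uninterpretable.** It adds ordinary chance variation, already counted in the standard error.
- **That a 10-point gap between arms moves IL-6 by 20% of the effect.** That figure belongs to a 10-point shift in the exercise arm's own share, which at a fixed total needs a 20-point gap.
- **That adjustment improves precision by 5%.** In the IL-6 simulation this is the reported SE of the centred-interaction model, which understates the true spread.
- **That handling stage would rescue power.** If the effect exists only in stage III, hs-CRP power at 60 falls from 91% with all stage III to 64%, 38% or 17% at 70%, 50% or 30% stage III. In an hs-CRP simulation at 50%, it was about 34-36% with or without stratification and adjustment. Dilution is a separate problem.

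**Conclusion.** The point holds as a modest, low-cost improvement. Stage is absent from both the strata and the model despite the pilot interaction and its availability before allocation. The consequence is a small loss of efficiency and of clarity in reading the result. The benefit of adding stage is about 1-2% in the IL-6 standard error and about 2 points of power, somewhat more if stage is also prognostic.

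These sizes rest on an assumed stage mix, a zero effect in stage I/II, and raw-scale figures, whereas the planned analysis is on log-transformed concentrations. They apply only if Phase 2 or 3 opened.

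**What to change.** In Statistical Analysis, before outcomes are analysed by arm, add stage (III versus I/II) as a covariate beside the baseline value and sex in the primary model. Cost: one sentence and one degree of freedom; no new data.

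Prespecify the group-by-stage term as a supportive analysis, with stage-specific estimates and confidence intervals, stating that the trial was not sized for it. If the term is instead centred and placed in the primary model, the standard error must allow for the sampled stage mix.

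Stratifying participants still to be randomized by sex and stage (four strata) is optional. It needs a change to the randomization list and protects only those not yet allocated, and the documents do not say how many remain.

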Protocol Title: The Exercise And Colorectal Cancer Treatment (EXACT) Trial

PI Name: [name]

Sub-Investigator's Name: [name]; [name]

Medical Investigator: [name]

Study-site contacts: [name]; [name]; [name]; [name]; [name]; [name]

Protocol Version Date: March 27, 2024 (Version 13)

Objectives

This randomized trial will examine the biological effects of 12 weeks of moderate-intensity aerobic exercise versus wait-list control in 60 subjects who have completed standard medical therapy for stage I- III colorectal cancer. The primary objective is to determine if aerobic exercise can reduce systemic inflammation, quantified using plasma concentrations of high-sensitivity C-reactive protein and interleukin-6. The secondary objectives are to determine if exercise can reduce 1) insulin resistance quantified using an oral glucose tolerance test and 2) circulating tumor cells quantified using a microfluidic antibody-mediated capture platform. The exploratory objective is to determine if exercise can improve mitochondrial respiration rates and fatty acid oxidation from peripheral blood mononuclear cells, and tumor fraction.

Background

Colorectal Cancer Prognosis. Each year, 145,600 people are diagnosed with colorectal cancer in the United States.¹ Despite efficacious surgical and chemotherapeutic interventions, 25–30% of patients will experience recurrent and metastatic disease within three years of diagnosis, and 91% of those who recur within three years die by five years.² Additional therapies are critically needed to maximize the likelihood of cure for these patients. One such additional therapy may be the prescription of physical activity.³

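### The planned IL-6 effect matches a pilot result reported for stage III only, so the stated 80% power depends on the stage mix, and stage appears nowhere in the design or analysis.

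*Combined protocol and SAP*

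**What the plan says.** The Power analysis section assumes an IL-6 baseline of 1.7 pg/mL (SD 0.7), a correlation of 0.58 between time points and "a reduction of -0.57 pg/mL in the exercise group over 12 weeks". It concludes that 48 participants give 80% power. No source is attached to the effect.

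Preliminary Data describes a three-arm pilot of 39 patients that ran against a "usual-care control group for 24 weeks". It says: "We identified an interaction between cancer stage (a randomization stratification factor in the pilot study) and randomized group", with P=0.051 for hs-CRP and P=0.002 for IL-6. The IL-6 change from baseline on 150 min/wk was -0.57±0.29 pg/mL, reported "in subjects with stage III but not in subjects with stage I/II disease". No stage I/II figure is given.

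The Objectives describe "60 subjects who have completed standard medical therapy for stage I- III colorectal cancer". Under Inclusion and Exclusion Criteria, Phase 1 takes stage III only. Then: "At the end of three months, if six subjects are not accrued, eligibility criteria will be expanded". Phase 2 changes the stage criterion: "Histologically-confirmed stage to include stage I, II, or III colorectal cancer". No expected or minimum stage III share is stated.

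Randomization is stratified by sex only. The Statistical Analysis section log-transforms the inflammatory markers, adjusts for the baseline value and sex, and tests IL-6 only after hs-CRP. It contains no stage term and no stage-specific estimate.

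**The concern.** The only stage-specific evidence in the protocol suggests that the IL-6 response differs by stage. The planning effect equals the figure from the stage in which a response was reported, yet the trial may enrol all three stages. If stage I/II patients respond less, the average effect in a mixed sample is smaller than the planned one, and power falls with the stage III share.

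Interpretation is also at stake. IL-6 is a co-primary outcome. A null result in a mixed sample could mean no effect, or an effect mainly in stage III, and the plan pre-specifies nothing that bears on which. The pilot stratified by stage; this trial neither stratifies by it nor models it.

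Two further differences belong to the same question of source. The pilot figure is a 24-week change within one arm, while the planning value serves as a 12-week difference between arms. They cannot be quantified, because the documents give no 12-week or between-group pilot estimate.

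**Working it through.** **Inputs.** From Power analysis: effect 0.57, SD 0.7, mean 1.7, correlation 0.58, 1:1 allocation, 60 enrolled. Two-sided 5% is assumed, because sidedness is not stated. My assumptions: all 60 analysed (30 per arm); stage III share s; stage I/II effect equal to a fraction f of the stage III effect, with f = 0 or 0.5.

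**The plan's own figure.** Normal approximation with the unadjusted SD: n per arm = 2(1.960+0.842)²(0.7/0.57)² = 23.7, rounded up to 24, so 48 in total. This matches the stated 48; the t-based total is 50. The match leaves out the stated correlation. With it, the t-based total is 42 for a change score or 34 for ANCOVA. All three variants are therefore carried forward.

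**SDs, raw scale (unadjusted / change score / ANCOVA).** 0.700 / 0.7√(2×0.42) = 0.642 / 0.7√(1-0.58²) = 0.570.

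**Log scale, as analysed.** Assuming lognormal IL-6, SD = √ln(1+(0.7/1.7)²) = 0.396. A fall from 1.7 to 1.13 is 34%, so the effect is ln(1.7/1.13) = 0.408. Applying the same multipliers and taking 0.58 as the log-scale correlation, the SDs are 0.396 / 0.363 / 0.322.

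**Diluted effect.** Mean effect = effect × [s + (1-s)f]. Power is from the noncentral t with 58 df and noncentrality mean effect/(SD√(2/30)). Example: log scale, s = 0.5, f = 0, ANCOVA: 0.204/(0.322×0.258) = 2.45, power 67%.

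| Stage III share | Stage I/II effect | Log scale, power % | Raw scale, power % |
|---|---|---|---|
| 100% | not applicable | 98/99/>99 | 87/92/97 |
| 75% | none | 84/90/95 | 64/72/81 |
| 75% | half | 93/96/99 | 77/84/91 |
| 50% | none | 50/57/67 | 34/39/48 |
| 50% | half | 84/90/95 | 64/72/81 |

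**Share needed for 80% power.** On the log scale, the smallest mean effect with 80% power at 60 is 0.291/0.267/0.237, which is 71/65/58% of 0.408. With f = 0 that percentage is the share needed. With f = 0.5 the share is (ratio-0.5)/0.5 = 43/31/16%.

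**Gatekeeping.** IL-6 is tested only if hs-CRP succeeds. The powers above are therefore upper bounds, and the shares needed are lower bounds.

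**What stage-specific estimates could show.** At a 50/50 mix (15 per cell, 56 df), the group-by-stage contrast has SE = SD√(4/15). Log-scale interaction power is 50/57/67% for f = 0 and 17/19/23% for f = 0.5. The 95% CI half-width for one stage is 2.003×SD√(2/15), or 0.24 to 0.29 log units against an effect of 0.408.

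**The case against.** The strongest reply is that the problem is conditional at every step.

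- **Source.** It is inferred from one matching number. Preliminary Data says only that the pilot informs the aims. This stands, so the point is worded as an inference.
- **Accrual.** Stage I/II patients enter only if stage III accrual is short. This stands: if accrual stays in Phase 1 there is no mismatch. The pilot accrued 5.5 per month, but from stages I-III, so that rate does not show that stage III alone will suffice. The Objectives name stage I-III without condition.
- **Scale.** The analysis is on logs with baseline adjustment. There, one quarter stage I/II with no effect, or one half with half the effect, still leaves power above 80%. This stands, and it limits the point to mixes with many stage I/II patients who respond well below half as much.
- **Headroom.** Sixty exceeds 48. The plan assigns that margin to dropout, recurrence and crossover, and the table already credits all 60.

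A reader might infer that the pilot showed no effect in stage I/II, so that the trial is underpowered for IL-6. The documents do not support this. Absence of a reported reduction in arms of 12 to 14 patients, split further by stage, is not evidence of zero effect, and no stage I/II figure is given.

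A reader might also extend the point to hs-CRP. Its planning value is -0.71 mg/L, against -0.79 for stage III in the pilot, and no source is given. The point reaches hs-CRP only if -0.71 is also a stage III value.

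**Conclusion.** The point holds in conditional form. The stated 80% IL-6 power is sound for a largely stage III sample and otherwise depends on a stage mix that the plan does not state. With no effect in stage I/II, the log-scale share needed is about 58-71% stage III; with half the effect it is 16-43%. At an even mix with no stage I/II effect, power is below 80% on both scales (50-67% log, 34-48% raw). At an even mix with half the effect, it is above 80% on the log scale and 64-81% on the raw scale.

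These figures rest on 60 analysed, lognormal IL-6, a 34% fall in stage III and a correlation of 0.58. The stage mix and stage I/II effect are scenarios, not estimates. The primary test remains valid. What is missing is a power statement tied to the population and a pre-specified look at the pilot's own effect modifier.

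**What to change.** 1. By dated amendment, before outcomes are seen by arm, add stage (III v I/II) as a covariate in the hs-CRP and IL-6 models. Pre-specify stage III and stage I/II effects with 95% CIs from a model with a group-by-stage term. Label them descriptive, given the low interaction power shown above.
2. In the Power analysis section, state the source of the IL-6 effect and qualify the 80% claim as applying to the stage III effect. Give log-scale power at the expected stage mix, with zero and half effect in stage I/II.

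Cost: one or two model degrees of freedom, a short power table and SAP wording. No new data are needed, since stage is confirmed before randomization. The downsides are imprecise stage-specific estimates and a less favourable power statement. The covariate helps with precision and chance imbalance; nothing here restores power lost to dilution.

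### Does the IL-6 sample size of 48 for 80% power contradict the inputs printed beside it?

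*Combined protocol and SAP*

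**What the plan says.** The Power analysis section of the combined protocol and SAP sizes the trial on two co-primary outcomes, with parallel sentences.

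- **hs-CRP:** the SD at baseline is 1.32 mg/L. The other inputs read "correlation of 0.8 between time points, a reduction of -0.71 mg/L in the exercise group over 12 weeks", with the error rate set at 5%. The stated result is that "46 participants total will provide 80% statistical power".
- **IL-6:** the section starts by "assuming a baseline concentration of 1.7 pg/mL with a standard deviation of 0.7 pg/mL". It then takes "a correlation of 0.58 between time points" for the two visits and, as the effect, "a reduction of -0.57 pg/mL in the exercise group over 12 weeks", again at the 5% level. The stated result is that "48 participants will provide 80% statistical power to detect between-group differences".

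Allocation is 1:1. The section names no test, does not say whether the 5% is two-sided, and gives no assumed change in the control group. It then inflates for dropout, recurrence and crossover, citing the pilot ("we observed a 3% dropout rate (defined as participants not providing endpoint data"), and concludes: "Enrolling 60 study participants provides a robust estimate of the largest necessary sample size needed for this trial".

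**The concern.** The two sentences have the same form, so one method should return both totals. The usual choice for an SD, a correlation between time points and a change is a t-test on change scores. It gives exactly 46 for hs-CRP but 42 for IL-6, six fewer than stated. Read the other way, 48 participants give about 85% power and not 80%.

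IL-6 is co-primary, and its 48 is the larger of the two base figures from which the 60 is built. If the 48 were a miscalculation, the basis for 60 would be in doubt. On the printed inputs the order of the two requirements also reverses, with hs-CRP needing more participants than IL-6. A reader cannot tell from the text whether the SD, the 48 or the 80% is the odd one out.

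**Working it through.** **Inputs (Power analysis section).** hs-CRP: SD 1.32, correlation 0.8, difference 0.71. IL-6: SD 0.7, correlation 0.58, difference 0.57. Both: 5% type I error, 80% power, 1:1 allocation. Assumed because the text is silent: two-sided test, no change in controls.

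**Method.** SD of change = SD × √(2(1 − r)); d = difference / SD of change; power from the noncentral t with N − 2 degrees of freedom and noncentrality d × √(N/4). N is the smallest even total that reaches the target power.

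**Step 1: reproduce the hs-CRP figure.** SD of change = 1.32 × √(2 × 0.2) = 0.835; d = 0.71/0.835 = 0.850. N = 46, power 80.5%. This matches the stated 46.

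**Step 2: same method for IL-6.** SD of change = 0.7 × √(2 × 0.42) = 0.642; d = 0.57/0.642 = 0.888. N = 42, power 80.2%. At 48, power is 85.4%. The stated 48 is not returned.

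**Step 3: other methods on the printed inputs.**

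| Method | hs-CRP (stated 46) | IL-6 (stated 48) |
|---|---|---|
| Change score, t, 80% power | 46 | 42 |
| Change score, t, 85% power | 52 | 48 |
| Baseline-adjusted, SD × √(1 − r²), t, 80% | 42 | 34 |
| Correlation omitted, normal formula, 80% | 110 | 48 |

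No row returns both stated figures.

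**Step 4: what the printed precision allows.** The IL-6 SD has one decimal, so 0.7 covers 0.65 to just under 0.75. With r = 0.58 and difference 0.57, by the method of step 1:

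| Unrounded IL-6 SD | N for 80% power |
|---|---|
| 0.70 | 42 |
| 0.72 | 46 |
| 0.737 | 48 |
| 0.7499 | 48 |

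At 0.74, for example, SD of change = 0.74 × √0.84 = 0.678, d = 0.840, and 48 participants give 81.3%. The stated 48 is therefore within the rounding of the stated SD. With the SD fixed at 0.70, rounding of the 0.58 and 0.57 alone gives only 42 to 44, so the SD is the input that matters.

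**Step 5: what the missing control-arm assumption allows.** The 0.57 is a reduction in the exercise group. The between-group difference is not printed. With SD 0.70 and r = 0.58, a difference of 0.531 to 0.541 returns 48. That is a control-arm fall of 0.57 − 0.541 = 0.029 to 0.57 − 0.531 = 0.039 pg/mL, with every printed input unchanged.

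**Step 6: does 60 hold?** A 3% dropout leaves 60 × 0.97 ≈ 58. Power by change score:

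| Outcome and inputs | N = 60 | N = 58 |
|---|---|---|
| IL-6, as printed | 92.3% | 91.4% |
| hs-CRP, as printed | 90.0% | 88.9% |
| IL-6, SD 0.75 (unfavourable rounding) | 88.5% | 87.3% |
| hs-CRP, correlation 0.75 (unfavourable rounding) | 82.6% | 81.2% |

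Every entry exceeds 80%. Dilution by crossover or recurrence is not included.

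**The case for a change.** The strongest case for acting is that a co-primary sample size should be checkable from its own inputs, and this one is not. If rounding is the explanation, the SD is printed too coarsely to support the 48. If it is not, either the 48 or the 80% is wrong. The repair is cheap: name the method, sidedness and control-arm assumption, and add a decimal.

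The arithmetic behind this stands. With the SD taken as exactly 0.70 and no control change, the change-score method does not give 48 at 80% power. Two of the ways to reach 48 would be real slips: powering IL-6 at 85%, or leaving out the correlation. The document does not exclude either.

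It does not point to them either. Both would mean that IL-6 was handled differently from hs-CRP, whereas the rounding route keeps one method for both outcomes. The benchmark is itself an inference. The change-score test is chosen because it returns 46, and with the other hs-CRP inputs as printed that match needs a correlation between about 0.7975 and 0.8065, when the text prints only 0.8. The worry about which outcome needs more participants has no practical force, since 60 covers both. Any request for correction would also have to leave every corrected figure blank, because the unrounded inputs are not in the document.

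**Conclusion.** No change to the plan follows. The IL-6 total of 48 cannot be reproduced from its rounded inputs, but it is not shown to be wrong. An SD of about 0.737 to just under 0.75, or a control-arm fall of about 0.03 to 0.04 pg/mL, returns it by the method that returns the hs-CRP 46. This is missing detail in a planning calculation. At face value the difference is six participants (48 against 42), or about five points of power (85.4% against 80%), and it errs on the safe side for IL-6. Enrolment of 60 gives more than 80% power for each outcome on its own, even at the unfavourable end of the rounding and after 3% dropout. The analysis, testing order and conclusions do not depend on the 48.

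This rests on a two-sided 5% test, a change-score comparison and, except where a control-arm fall is named, no change in controls. None of these is stated in the section. It does not address dilution of the effect by crossover or recurrence.
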